A key challenge to the effectiveness of extended-care programs has been continued participant engagement, typically operationalized as session attendance. Attendance has been consistently associated with long-term weight loss maintenance;  however, attendance at monthly extended-care sessions tends to be poor and declines over time.  The once-per-month, static treatment schedules of existing programs may contribute to these suboptimal outcomes.  Under this schedule, a participant experiencing a small lapse (e.g., failing to self-monitor dietary intake for several days) may not receive additional support for several weeks, by which time they may be experiencing a larger lapse (e.g., complete abandonment of self-monitoring and former dietary changes) and weight regain. Importantly, this cycle may result in participant disengagement and avoidance of treatment sessions due to feelings of frustration, shame, or embarrassment.  In contrast, tailoring intervention delivery such that extended-care sessions are provided when individuals are at "high risk" for weight regain offers potential to disrupt this cycle and significantly improve program engagement, adherence to program goals, and long-term weight maintenance outcomes.

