whose data were not used to develop the predictive algorithm. In this separate test dataset, the algorithm demonstrated a sensitivity of 82.0% and a specificity of 30.4%. Taken together, these promising results suggested two key implications: 1) that weight regain can be reliably modeled and predicted, and 2) that this optimized predictive algorithm demonstrated good performance both in the initial training and separate testing datasets.

In the current study, we propose to evaluate an innovative method of providing phone-based extended-care treatment *adaptive to participant needs*. The proliferation of smartphones and mHealth apps has allowed for the development of new, adaptive treatment models aimed at providing intervention when it is needed most. Monitoring early signals of weight regain via an mHealth app will allow us to tailor intervention delivery at a previously-impossible level, via a method that is convenient and acceptable to participants. The dataset resulting from the current trial will be unique in terms of both *scope* and *resolution*, allowing us to build innovative behavioral models to inform future just-in-time adaptive intervention development.

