# 5. Specific Aims:

**Aim 1:** Test the hypothesis that *ADAPTIVE* participants will experience significantly less weight regain than *STATIC* participants between Month 4 (randomization) and Month 24.

**Aim 2**: Test the hypothesis that, compared to *STATIC*, a significantly greater proportion of *ADAPTIVE* participants will maintain clinically significant (≥ 5% from baseline) weight losses at Month 24.

**Exploratory Aims:** We propose to 1) use daily weight data collected via our mHealth app to model differences in weight trajectories between groups; 2) investigate potential treatment mediators (e.g., treatment engagement/session attendance and adherence to diet, physical activity, and self-monitoring goals); 3) use the rich dataset collected via our mHealth app to develop dynamic models of weight loss/regain and to investigate additional proximal predictors of weight-related behaviors, identifying potential decision points and tailoring variables for future just-in-time adaptive intervention development.

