MyTrack+ will link with the FatSecret application through an API link, using a de-identified study ID to link participant self-monitoring data and display this data within the MyTrack+ application. Further, MyTrack+ will send prompts to study participants asking them to complete brief questionnaires (see full description in the measures section). All randomized participants will receive extended-care intervention delivered via phone; however, the frequency/timing of these calls will vary between the ADAPTIVE and STATIC conditions. Similar to protocols for phone-based intervention sessions previous trials conducted by the PI and the ongoing Rural LEAP trial, each phone-based extendedcare session will last for approximately 10-20 minutes. Each call will be initiated by the interventionist. and will begin with a brief check-in followed by a discussion of any barriers experienced by participants in meeting their weight maintenance goals. To address these barriers, interventionists will guide participants through a five-step problem solving model, 35 including 1) positive problem orientation (developing a positive mindset), 2) problem definition (the concrete definition of the problem; i.e., the who, what, when, where, and why of the problem), 3) generation of alternatives (a brainstorming session where the goal is to produce the maximum number of potential solutions), 4) decision making (the evaluation of potential solutions by two key criteria: "will this work if I do it?" and "what are the odds I'd actually do it?") and 5) solution implementation and verification (i.e., trying out the proposed solution and evaluating effectiveness). Each call will end with a formal goal setting session wherein participants are encouraged to set SMART (Specific, Measurable, Achievable, Relevant, and Time-limited) goals. Interventionists will keep notes on each session so that he/she can check in with each participant during the next call regarding success toward stated goals (and success of any problem solutions identified). Further, the start and end time of each call will be documented to monitor the frequency/duration of intervention calls, and each call will be audio recorded to monitor intervention fidelity.

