If the participant cannot be reached for a call, the interventionist will leave a voicemail asking the participant to return his/her call. Interventionists will make up to 5 "call attempts" on various days/times (ideally no more than one call per day) if unsuccessful. If the participant cannot be contacted after 5 attempts, the interventionist will attempt to contact the individual via email to note difficulty reaching the participant. If the interventionist does not receive a response to the email within a week, he/she will send a certified letter to the participant's home address noting the difficulty contacting them and to encourage continued participation in the study.

**STATIC** Extended-Care Program. Participants randomized to the *STATIC* maintenance program will receive the extended-care intervention phone calls described above on a fixed, once-per-month schedule. The initial call date/time will be scheduled during each participant's randomization notification call. At the end of the initial phone session (and each session thereafter), interventionists will confirm the next call's scheduled day/time (one month after the current call, at the same time) and reschedule if necessary (e.g., participant time conflicts due to work or travel).

**ADAPTIVE** Extended-Care Program. For participants randomized to the *ADAPTIVE* maintenance program, the extended-care intervention phone calls described above will be delivered only if either 1) an algorithm developed by our study team detects that a participant is at "high risk" for weight regain or 2) the participant self-initiates a request for a session by navigating to a "support" section of the app. The algorithm that will be used to trigger intervention is provided in Figure 1; the collection of data required for this algorithm will be conducted via MyTrack+ and is described in detail in the measures section.

Once intervention has been triggered (via our algorithm or an in-app support request), a notification

will be automatically sent to the participant's interventionist via a secure email, and the interventionist will initiate an intervention call as soon as possible (i.e., at the next day/time the participant indicated they were generally available for intervention calls). On weeks that intervention is not triggered via our algorithm or via in-app participant request, no additional intervention contact will be provided.

[figure not shown]

Figure 1. Final ADAPTIVE Treatment Delivery Algorithm

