*ADAPTIVE* and *STATIC* groups over time. Changes in dietary intake, physical activity, and self-monitoring adherence over time will be assessed using multilevel models for repeated measurements. Potential treatment meditators (e.g., intervention engagement, operationalized as the proportion of possible extended-care sessions attended, adherence to self-monitoring, and changes in dietary intake/physical activity) will be assessed using bootstrapping to estimate confidence intervals around indirect effects. Finally, the rich dataset collected via MyTrack+ (including time-stamped self-monitoring data (including not only frequency counts of self-monitoring behavior but also daily weight, caloric intake, and physical activity data) and ecological momentary assessment questionnaire data collected over a full two year study period) will be used to examine proximal predictors of change in weight and weight-related behaviors. Following the pragmatic framework developed by Nahum-Shani and colleagues, we propose to build dynamic models of weight loss and weight regain, identifying key tailoring variables and potential intervention options for future just-in-time adaptive interventions for weight loss maintenance.

The most recent clinical guidelines for the treatment of obesity (released as a joint report by the American College of Cardiology [ACC], American Heart Association [AHA] and The Obesity Society [TOS]) $^{10}$  define 2.5 kg as the *minimal* amount of weight loss associated with lowered risk of type 2 diabetes, and further note that weight losses of this magnitude are associated with modest improvements in triglycerides, and modest reductions in blood pressure. Thus, similar to previous weight management trials powered to detect this smallest clinically-meaningful difference, $^{3,28}$  sample size for the primary aim analysis was selected to provide a statistical power of .90 to detect a difference in weight change of  $2.5 \pm 5.5$  kg between groups from Month 4 to Month 24. This resulted in an estimated 206 participants (103 participants per group). With SDs of 5.0 and 6.0, estimated power would be .946 and .845, respectively. Assuming a retention rate of 80% at Month 24, 258 participants would need to be randomized at Month 4.

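### Does defining engagement as the proportion of possible sessions attended spoil the exploratory mediation analysis?

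*Combined protocol and SAP*

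**What the plan says.** Mediation is an exploratory aim. *Specific Aims* proposes to "investigate potential treatment mediators (e.g., treatment engagement/session attendance and adherence to diet, physical activity, and self-monitoring goals". *Statistical Design and Power* gives the working definition, "intervention engagement, operationalized as the proportion of possible extended-care sessions attended", within a list that is introduced by way of example, and tests indirect effects with bootstrap intervals.

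The Background supplies the rationale. It names as a key challenge "continued participant engagement, typically operationalized as session attendance", and describes a cycle in which a lapse without timely support leads to "participant disengagement and avoidance of treatment sessions due to feelings of frustration, shame, or embarrassment".

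*Intervention and Randomization* says that "the frequency/timing of these calls will vary between the ADAPTIVE and STATIC conditions". STATIC calls come "on a fixed, once-per-month schedule". ADAPTIVE calls follow an algorithm trigger or an in-app request, and a week with neither brings no contact. The same section records that "the start and end time of each call will be documented to monitor the frequency/duration of intervention calls". *Data collected through the study* adds that app usage is collected to assess engagement.

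**The concern.** The denominator is not defined by arm. In STATIC it can be inferred from the monthly schedule. In ADAPTIVE it arises after randomization, and two cases have no stated rule: a new trigger while an earlier contact cycle is still open (up to five attempts, then an email and a week's wait), and a participant who never triggers, for whom the proportion is 0/0.

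A proportion is also not an amount. If ADAPTIVE helped because it delivered more calls, a mediator on the rate scale would not show it. If ADAPTIVE participants attended a smaller share of many more calls, the indirect effect through the proportion would even point towards regain. At stake would be the explanation of a positive trial: better timing, better engagement or simply more contact.

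**Working it through.** The plan gives no expected call count and no power for this mediator, so there is no figure of its own to reproduce.

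**1. How far apart can rate and contact be?**
- Month 4 to Month 24: 20 × 365.25/12/7 = 86.96, about 87 weeks. STATIC therefore has about 20 calls.
- The Background reports that in the test dataset "the algorithm demonstrated a sensitivity of 82.0% and a specificity of 30.4" percent, without stating the unit. Assume it applies per participant-week. The weekly trigger share then lies between 1 − 0.304 = 0.696 and 0.82, giving 0.696 × 86.96 = 60.5 to 0.82 × 86.96 = 71.3 triggers.
- At an assumed 80% attendance: STATIC 20 × 0.8 = 16 calls; ADAPTIVE 48.4 to 57.0. If 10% of weeks triggered, 8.7 × 0.8 = 7.0.
- The denominators are equal only if 20/87 = 23% of weeks yield a call.

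So the proportion does not measure contact, and the direction of any difference in contact is open.

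**2. Does the proportion give a wrong answer to its own question?**

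Let regain be y = b × calls + noise, with calls = offers × attendance rate, and choose b so that the total effect is −2.5 kg. Mean offers are 20 in STATIC and 87 × 0.75 = 65.25 in ADAPTIVE (32.625 if half of triggers become offers). The true effect through attendance rate is b × offers × (ADAPTIVE rate − STATIC rate), with offers held at the STATIC or the ADAPTIVE level. For 70% vs 60%: calls are 14 and 39.15, so b = −2.5/25.15 = −0.0994. The effect is 20 × (−0.10) × (−0.0994) = +0.20 kg, or 65.25 × (−0.10) × (−0.0994) = +0.65 kg. The other rows follow in the same way.

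| STATIC vs ADAPTIVE attendance | b (kg per call) | True effect through rate (kg) | Simulated estimate (kg) |
|---|---|---|---|
| 70% vs 70% | −2.5/31.675 = −0.0789 | 0 | 0.00 (SD 0.08) |
| 70% vs 60% | −0.0994 | +0.20 to +0.65 | +0.41 (SD 0.26) |
| 70% vs 50% | −2.5/18.625 = −0.134 | +0.54 to +1.75 | +1.11 (SD 0.49) |
| 70% vs 60%, half offered | −2.5/5.575 = −0.448 | +0.90 to +1.46 | +1.18 (SD 0.38) |
| 60% vs 75% | −2.5/36.94 = −0.0677 | −0.20 to −0.66 | −0.38 |

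The simulation used 103 per arm and residual SD 5.5 kg. Attendance was Beta with parameters 10m and 10(1 − m) for mean m. ADAPTIVE offers were binomial over 87 weeks, with a weekly trigger probability of mean 0.75 and SD 0.08. The indirect effect was the arm difference in the mediator times its within-arm slope.

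Every estimate has the right sign and lies within the true range. A positive value is not an error: if ADAPTIVE participants attend a smaller share of calls, the attendance rate really does work against them, and the benefit comes from the larger number of offers.

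**3. Would call count do better?**
- Suppose attendance rate carries the benefit (60% vs 75%). The proportion returns −2.50 kg (SD 0.52), as it should. Completed calls, which by construction add nothing beyond the rate, return −8.90, −5.17 or −0.14 kg with all, half or a quarter of triggers offered.
- Suppose calls carry the benefit (70% vs 70%, all triggers offered), but latent risk, which drives triggers, also adds regain. The call-count estimate moves from −2.46 kg with no confounding to −1.38, −0.24 and about +0.84 kg as risk adds 1, 2 and 3 kg per SD. The truth is −2.5 kg throughout.
- Even without confounding, call count and arm correlate at 0.89. The estimate has SD 1.43 kg, and its interval excludes zero in only 41% of trials.

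**The case for a change.** The best case for a change is that an undefined denominator invites a choice after the data are seen. If 60.5 calls are triggered and 48.4 completed, the proportion is 48.4/60.5 = 0.80 of triggered calls but 48.4/87 = 0.56 of all weeks, so two analysts could build different mediators from one dataset. Readers of a positive result will also ask whether ADAPTIVE simply delivered more calls. The call logs exist, so the remedy costs only wording.

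Part of this stands. The text does not cover repeat triggers or the participant with no trigger, and an attendance rate must not be reported as contact received. The rest is weaker. Counting all weeks sits badly with the rule that an untriggered week brings no contact; the natural reading is calls due in STATIC and calls triggered or requested in ADAPTIVE. A 0/0 participant should be rare: even at a 10% weekly trigger rate with independent weeks, 0.9^87 is about 0.0001. The delivery algorithm's figure is not reproduced in the text available here, so it may already settle repeat triggers. Calls and minutes are logged, and an open-ended mediator list does not bar their use. Describing them by arm would help a reader, but it would not separate frequency from timing, which the two-arm comparison tests together.

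**Conclusion.** No change to the plan is needed. The missing denominator is a detail of an exploratory analysis that analysts can settle sensibly from the call schedule. The proportion is a valid attendance-rate mediator and matches the Background's theory; it misleads only if read as contact received, a label the plan does not give it. Making call count a named mediator is a matter of preference with its own hazard, since confounding by regain risk can shrink its estimate to nothing or reverse its sign.

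Nothing in Aim 1, Aim 2, the power or the sample size depends on this. The kilogram figures rest on assumed attendance rates, trigger rates and shares of triggers turned into calls, none of which the documents give. They show direction and are not forecasts. The conclusion that the proportion answers its own question does not depend on those values: when regain depends on calls and calls are offers times rate, the effect through rate takes the sign of the attendance difference.

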## **Data and Safety Monitoring Plan**

Given that participants are not masked to intervention condition, vulnerable populations will not be enrolled, and this is a Phase II trial with minimal risks, we propose that the safety monitoring of the study will be conducted by [name], the study Safety Officer. [name] is a clinical psychologist and a Professor and Associate Department Chair in the Department of Clinical & Health Psychology at the University of Florida. His previous experience as principal investigator or coinvestigator on over 15 clinical trials (many of which focused on behavioral approaches to improving diet and physical activity) renders him well qualified to review aspects of the progress and safety of this trial. Information regarding progress with recruitment, retention at assessment sessions, reasons for dropout, and adverse events will be submitted once per year to the Safety Officer for review. After reviewing this data, the Safety Officer will indicate in writing to [name] and NIH whether the study is progressing appropriately or changes are needed. At any point during the trial, the Safety Officer can recommend that a phone call be held to discuss any issues with the progress or safety of the trial.

All of the staff involved in data collection will be trained by the Principal Investigator ([name]) and/or the Research Coordinator and must demonstrate competence in administering all measures. Study Research Assistants (masked to treatment condition) will review all assessment data for accuracy and completion, and the Lab Manager along with the Graduate Assistant in Biostatistics/Data Manager will monitor data entered into the REDCap system by participant self-report or by research staff and completion of ASA24 recalls via the National Cancer Institute online ASA24 portal. Participants will be re-contacted to provide missing data or to clarify ambiguous responses. Range checks will be built into the data entry procedure to alert staff to data that should be clarified. Under the supervision of the Research Coordinator and the Lab Manager, a complete double-entry verification procedure will be used for all data entered to ensure accuracy. Under the supervision of the Co-Investigator/study statistician ([name]), the Graduate Assistant in Biostatistics/Data Manager will conduct error checking and preliminary analyses of all data to further ensure accuracy. Any existing hard copies of data will be stored in a locked filing cabinet in a locked room, and electronic data files will be password protected and backed up on a secure UF server.

All participant records and assessment data will be treated as confidential, including participants' names and the fact that they are participating in the study. Participant information collected by the research staff will contain only a non-identifiable study ID. A separate database linking study ID and participant identifiers (name, address, contact names and addresses) will be maintained in an encrypted, password-protected file stored on a secure UF server. Records and assessment data will be safeguarded according to the policy of UF's IRB, which promotes the protection of confidential health information.

All study workstations will be managed by UF Information Technology (IT), (workstations located in the Health Professions, Nursing, and Pharmacy building and the Dental Ground floor area of UF Health Shands Hospital will be managed by the College of Public Health and Health Professions IT, and workstations located in the Department of Computer and Information Science and Engineering (CISE) will be managed by CISE IT), patched regularly, will have lock screens that automatically engage at 15 minutes idle time. All study workstations will utilize GatorLink accounts for access, and study databases stored on these workstations will be encrypted and password protected. Only IRB-approved research team members will have access to study databases. Data will be encrypted during transfer from BodyTrace and FatSecret and when stored on UF servers. Participants will be assigned a unique, non-identifiable study identification number that will be used to link data from BodyTrace, FatSecret, MyTrack+, REDCap, and study databases.

Additional safeguards are in place to protect participant questionnaire data entered via REDCap. The REDCap platform is managed by the UF Clinical and Translational Science Institute and only IRB-approved research team members will have access to the platform. REDCap system security includes: secure logins, data encryption at rest, remote system logging and configuration and change management. Each team member is granted access to REDCap through a secure login, and audit trails are available by username. Data backups are encrypted both in flight and at rest.

### 7. Possible Discomforts and Risks:

### a. Potential Risks

The extensive literature on behavioral interventions for weight loss shows that there are very few risks associated with this type of intervention, provided that energy intake exceeds 1,000 kcal/day. In the proposed study, participants are encouraged to follow a balanced diet above this minimum amount (our targeted goals encourage participants to consume 1,200 to 1,800 kcal/day, based on initial weight). This study asks some participants to monitor their weight daily; while this may raise concerns of negative psychological reactions (e.g., lower body image, depression), research has demonstrated that daily self-weighing does not negatively impact individuals. There is a small potential risk of musculoskeletal injury associated with the exercise component of the intervention. In the Diabetes Prevention Program, on which the current initial intervention is based, the occurrence of musculoskeletal injuries was 3% higher in the lifestyle intervention group than in the placebo control condition. In our studies, we have found that the risk of injury from exercise can be minimized through the use of moderate- rather than high-intensity exercise activities. The procedures to minimize risk are described in further detail below.

